10.0 EVALUATION DURING TREATMENT/INTERVENTION

All patients will be evaluated according to the standard of care for their head and neck cancer.

11.0 TOXICITIES/SIDE EFFECTS

No side effects are expected as a result of this study. However, in the unlikely event that an adverse reaction to either radiopharmaceutical occurs, these toxicities will be graded according to Common Terminology Criteria for Adverse Events (CTCAE) version 4.0. The results will be documented and reported by the Principal Investigator to both the Institutional Review Board and the IND Committee chairmen.

Cohort 1 patients who will have optional ¹⁸F-FMISO PET image-guided core biopsies might experience the following:

Likely

- Discomfort when the needle enters into your neck
- Minimal if any bleeding from your neck

Less Likely

- Infection
- Neck pains

Cohort 2 patients who undergo neck dissection might experience the following:

Likely

- Temporary postoperative discomfort
- Numbness of the skin
- Visible healed scar line

Less Likely

- Scar tissue (fibrosis) of the neck leading to tightness

- Infection

Rare but serious

- Fluid collection in the neck requiring drainage (seroma)
- Bleeding (hematoma) requiring a second surgery
- Loss of function of a nerve (lower lip asymmetry, shoulder dysfunction, hoarseness, others)
- Chyle leak (prolonged fluid drainage from the neck)

Patients who partake in the optional storage and analysis of tissue samples will not have additional risks or toxicities other than the unauthorized and inadvertent release of PHI.

Gadavist, a gadolinium-based contrast agent, is the standard contrast agent utilized in contrast MRIs. However, adverse reactions to gadolinium-based contrast agents have been documented, which may include headaches, rash, and itching. Furthermore, gadolinium-based contrast agents are associated with a risk for Nephrogenic Systemic Fibrosis (NSF) and renal failure. Due to these associated risks, subjects enrolled on this protocol with a known contraindication to the standard MRI contrast agent (Gadavist, a gadolinium-based contrast agent) and/or a recent estimated glomerular filtration rate (eGFR) of 30 or less will be excluded from all DCE-MRIs, and will instead receive non-contrast MRIs at the DCE-MRI time points.

12.0 CRITERIA FOR THERAPEUTIC RESPONSE/OUTCOME ASSESSMENT

Not applicable.

13.0 CRITERIA FOR REMOVAL FROM STUDY

If at any time the patient develops progressive disease he/she will be taken off study and referred for alternative therapy. If at any time the patient develops unacceptable toxicity he/she will be removed from study.

If at any time the patient is found to be ineligible for the protocol as designated in the section on Criteria for Patient/Subject Eligibility (i.e., a change in diagnosis), the patient will be removed from the study.

If at any time a patient wishes to participate in the optional sub-study regarding additional banking and analysis of tissue via the optional biopsy (Cohort 1) or via the standard of care surgical resection (Cohort 2), the patient has a right to withdraw participation and prohibit any future use of their biologic specimen that has not already been undertaken. If the specimen has already been sent out from the archive for research purposes, it cannot be excluded from the research, nor would any results derived from the research activity be excluded.

As ^{18}F -FDG PET scans are routinely obtained before and after chemoradiation for head and neck cancer, we will include a prospective MTV (metabolic tumor volume) calculation in addition to the already calculated standard uptake value (SUV) for the routine ^{18}F -FDG PET scans. We will not alter any patient management based on the calculated MTV. The MTV, defined as tumor volume with 42% or greater of the maximum ^{18}F Fluorine-fluoro-deoxyglucose (^{18}F -FDG) signal intensity on positron emission tomography (PET), has been demonstrated to correlate with loco-regional control, freedom from distant metastases, and overall survival in oropharyngeal cancer patients treated with definitive chemoradiation therapy at MSKCC (21). These findings corroborate those of previously published retrospective studies from Stanford Medical Center (22, 23).

Biostatistics for HPV+ tumors with no evidence of hypoxia on their baseline ^{18}F -FMISO PET/CT or that exhibited hypoxia resolution on their early repeat ^{18}F -FMISO PET/CT.

100 HPV+ patients with negative baseline scan or early resolution of tumor hypoxia of their node(s) at 5-10 treatment days into chemoradiation, defined by an absence or disappearance of ^{18}F -FMISO uptake on PET/CT, will achieve an equivalent nodal control with nodal radiation dose at 60Gy in the setting of chemotherapy with concomitant reduction in treatment-related complications. To test if patients receiving 60Gy to the node(s) followed by an FDG PET and observation similar treatment outcomes when compared to the radiation of 70Gy to the nodes both in the setting of concurrent chemotherapy, we will apply a one-sided one sample proportion test. Our past experience is that the nodal control rate at 3 months for such patient with 70Gy to the nodes is 94%. We will reject our hypothesis of equivalent control whether patients receive 70Gy to the nodes or 60Gy to the nodes followed by an FDG PET and observation if ≤ 57 patients out of the 66 in total who received 60Gy to the nodes achieve the same 3-month nodal control after chemoradiation. With this rule, we have a power of 0.93 for detecting that 60Gy will result in 3-month regional control lower than 80% with the type I error rate lower than 0.05. To test if patients receiving 60Gy to the nodes followed by an FDG PET and observation show superior toxicity outcomes when compared to the historical results from similar patients receiving 70Gy, we will apply a one-sided one sample proportion test. Grade 2 or higher toxicities that occurred within 3 months from the completion of IMRT will be counted in this analysis. Our past experience is that this toxicity rate for patients receiving 70Gy is around 75%. Using the total of 66 patients that undergo 60Gy to the nodes, we will reject our hypothesis of equivalent or higher toxicity rate when the nodes receive 10Gy less radiation from 70Gy when ≤ 43 patients have at least one \geq grade 2 toxicities. With this rule, we have a power of 0.84 for detecting the probability of 60% of patients will have at least one \geq grade 2 toxicity with the type I error rate lower than 0.05. Effort will be made to monitor all toxicities occurring beyond 3 months from chemotherapy and IMRT for all patients. However, censoring can be an issue so we will not apply the proportion test for toxicities after 3 months from chemoradiation. Instead, we will summarize the data descriptively and when applicable, we will use survival analysis tools such as Kaplan-Meier estimation and log-rank tests to determine whether 60Gy results in lower toxicity. To examine the potential correlations between various evaluation methods for nodal control status, we will apply a series of Fisher's exact tests.

The spatial extent of ^{18}F -FMISO PET imaging within the neck node(s) determines the underlying hypoxia tumor phenotype for both HPV positive and negative HNSCC. To determine whether baseline ^{18}F -FMISO PET/CT and/or early-response ^{18}F -FMISO PET/CT at 5-10 treatment days after chemotherapy and IMRT correlate with selected proliferative/hypoxia molecular markers, Wilcoxon rank sum tests will be used for each marker. Multiple testing adjustments such as Bonferroni procedures will be used. To investigate whether the extent of ^{18}F -FMISO PET/CT measured hypoxia at baseline and/or 5-10 treatment days into chemoradiation for both HPV positive and negative tumors correlates with the development of distant metastasis, Kaplan-Meier estimates will be calculated for each stratum and compared using the log-rank tests. When competing risks are present, Gray's test will be used to examine the correlation between the extent of ^{18}F -FMISO PET/CT measured hypoxia with the development of distant metastasis. To examine the potential correlations between the baseline and early

response ¹⁸F-FMISO PET imaging and tumor's underlying HPV status, we will apply Fisher's exact tests.

Multiparametric scans will also be obtained. We will attempt comparisons to ¹⁸F-FMISO PET results and immunohistochemistry hypoxia results, but due to the small pilot size of this exploratory aim, we may not produce significant results. In that case, we will present summary statistics and suggest directions for future study.

> For this study cohort, 14 eligible patients will be needed for the analysis. Assuming approximately 25% of the patients enrolled will not be eligible, we will plan to recruit 19 patients upfront. For evaluation on the efficacy of the regimen in this cohort, a simple decision rule will be implemented, which is as follows: If, among the total 14 eligible patients, we have at least 10 patients who are alive, followed and have a pathologic CR at 4 months from the end of the treatment, then we will declare the treatment modality using 30 Gy is feasible and worthy of further investigation. Any patient who died or is lost to follow up within 4 months from the end of radiotherapy will be regarded as a failure, i.e., without pathologic CR. Feasibility for the primary objective in cohort 2 will be defined according to aforementioned decision rule. This decision rule has the following probabilities of declaring success.

True Locoregional Control Rate									
0.50	0.55	0.60	0.65	0.70	0.75	0.80	0.85	0.90	
Probability of Declaring Success									
0.090	0.167	0.279	0.423	0.584	0.742	0.870	0.953	0.991	

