2.0 OBJECTIVES

Primary

- To improve the accuracy of hypoxia imaging for head and neck cancers through pixel by pixel kinetic analysis of ^{18}F -FMISO tracer of dynamic PET images (Cohort 1 and Cohort 2).
- To detect on repeat ^{18}F -FMISO PET/CT scans whether there is a reduction of the ^{18}F -FMISO-avid or GIV_h 5 to 10 days into treatment with standard chemoradiotherapy for a series of locally advanced head and neck cancers (Cohort 1).
- To show that it is feasible to deliver 70Gy to primary site and 60Gy to the neck nodes in HPV+ patients who exhibit no evidence of hypoxia on their baseline ^{18}F -FMISO PET/CT scans or those who have early resolution of hypoxia on their early repeat ^{18}F -FMISO PET/CT scans (Cohort 1).
- To show that it is feasible to deliver 30Gy to the surgical bed and neck nodes in low-risk HPV+ patients who exhibit no evidence of hypoxia on their repeat ^{18}F -FMISO PET/CT (Cohort 2).
- To correlate the intensity of the ^{18}F -FMISO PET signal with the degree of immunohistochemical staining of hypoxia biomarkers for tissue obtained via biopsy (Cohort 1) and surgical resection (Cohort 2): HIF-1 α , Lysyl Oxidase, and Ki67 (an independent marker of tumor aggressiveness), among others.

Secondary

- To compare tumor heterogeneity derived from pixel-by-pixel kinetic analysis of PET scan and DWI-MRI (Cohort 1).
- To assess changes in tumor heterogeneity over the course of external beam RT using serial multiparametric MR and DCE-MRI scans (Cohort 1).
- To determine the potential of DCE-MRI data as a priori or early markers of tumor response to chemoradiation as well as long term disease-free survival after treatment (Cohort 1).
- To assess normal tissue response as a function of dose for parotid, submandibular glands, muscles and bones in the head and neck region during and after EBRT using serial multiparametric MR scans (Cohort 1).
- To bank specimens for further IRB/PB approved exploration of genetic analysis (Cohort 1 and Cohort 2).

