At our institution, we have an active hypoxia imaging protocol, MSKCC IRB# 04-070, for all head and neck tumors regardless of HPV status. The first 20 head and neck cancer patients that were enrolled in this protocol were all treated with 70Gy to both the primary site and the neck nodes. An exceptionally high locoregional control rate of 95% was seen with a nodal control rate of 95% as well (9). Furthermore, all but two patients had resolution of their baseline hypoxia on repeat ¹⁸F-FMISO PET/CT imaging.

When considering the evidence regarding HPV status and the effects of hypoxia on tumor response, it can be inferred that oropharyngeal carcinoma patients with the most superior prognosis are those who meet the following criteria: HPV-related and no evidence of hypoxia. Therefore, given: (1) the rise in HPV-related oropharyngeal carcinoma, (2) the significance and burden of oropharyngeal carcinoma treatment-related toxicities, and (3) in-house data where hypoxia response correlated with high loco-regional control, the current version of this protocol seeks the following for select patients in Cohort 1 (patients receiving chemoradiation without surgical resection):

- A. to give HPV+ oropharyngeal carcinoma patients who demonstrate no evidence of hypoxia on a ^{18}F -FMISO PET/CT scan the option of an alternative standard approach to the treatment of oropharyngeal carcinoma through delivering 60Gy to the neck nodes followed by a FDG PET/CT scan. The primary site will receive 70Gy, and these patients will undergo standard chemotherapy regimens. Delivering 60Gy to the neck nodes followed by a FDG PET/CT scan and continued observation does not deviate from one current standard of care, and allows for the ability to deliver a lower dose of radiation to the neck with the goal of minimizing radiation toxicities while ensuring that no unwarranted compromise to the already excellent loco-regional control in this population occurs. All the imaging studies will be done exactly per protocol.

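### The Cohort 1 nodal-control test makes equivalence to 94% the null hypothesis, so 60Gy is supported only by failure to reject; the hypotheses should be reversed, with a stated and justified margin

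*Combined protocol and SAP*

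**What the plan says.** Section 14.0 Biostatistics, in the part on HPV+ tumors with absent or resolved hypoxia, opens with the expectation that these patients "will achieve an equivalent nodal control with nodal radiation dose at 60Gy in the setting of chemotherapy". A one-sided one-sample proportion test follows, with a reference rate of 94% taken from past experience with 70Gy.

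The decision rule is: "We will reject our hypothesis of equivalent control whether patients receive 70Gy to the nodes or 60Gy to the nodes" when no more than "57 patients out of the 66 in total who received 60Gy to the nodes achieve the same 3-month nodal control after chemoradiation". Its operating characteristics are given as "we have a power of 0.93 for detecting that 60Gy will result in 3-month regional control lower than 80" per cent, with type I error below 0.05. The plan does not say what is concluded when 58 or more are controlled.

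The toxicity test in the same section runs in the other direction: "we will reject our hypothesis of equivalent or higher toxicity rate when the nodes receive 10Gy less radiation from 70Gy" when 43 or fewer of 66 have a grade 2 or higher toxicity. There, the favourable conclusion requires a rejection.

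Section 3.0 states the purpose as lowering the neck dose "while ensuring that no unwarranted compromise to the already excellent loco-regional control in this population occurs". Section 2.0 words the primary objective as feasibility: "To show that it is feasible to deliver 70Gy to primary site and 60Gy to the neck nodes in HPV+ patients".

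**The concern.** The claim of interest is that control is not materially worse with 60Gy. The test makes that claim the null, so the data can contradict it but cannot establish it. With 66 patients, a result compatible with a considerable loss of control would still be carried forward as equivalent.

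The error rates are also assigned the wrong way round for a no-detriment question. The 0.05 limit protects against wrongly abandoning 60Gy. The error that matters to later patients, keeping the equivalence claim when control has fallen, is limited only indirectly, as 1 minus the stated power, and only at 80%.

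The 80% is never called a margin and no reason is given for it. It implies that a loss of 94 − 80 = 14 percentage points is the boundary of interest. The 94% is treated as a fixed value, and neither its sample size nor an interval is given.

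**Working it through.** **Inputs (all from Section 14.0).** n = 66; reject equivalence if X ≤ 57; reference rate 0.94; alternative 0.80; stated power 0.93; stated type I error below 0.05. X is the number with nodal control at 3 months, X ~ Binomial(66, p).

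**1. Reproduce the plan's figures.**
- Type I error = P(X ≤ 57 | p = 0.94) = 0.0168 (stated: below 0.05).
- Power = P(X ≤ 57 | p = 0.80) = 0.9318 (stated: 0.93).

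The figures agree with 94% as the null and 80% as the alternative. The toxicity rule also reproduces: P(X ≤ 43 | 0.75) = 0.048 and P(X ≤ 43 | 0.60) = 0.836 (stated 0.84). The arithmetic is sound; the problem is the direction of the nodal-control test.

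**2. What the boundary result would show.** At 58/66 = 87.9% equivalence is retained. The exact (Clopper-Pearson) one-sided 95% bounds are 79.2% below and 93.8% above. The lower bound does not exclude 80%, and the upper bound does exclude 94%. Equivalently, P(X ≤ 58 | 0.94) = 0.043, below the plan's own 0.05. Read as a test against 80%, the 58-or-more rule has type I error P(X ≥ 58 | 0.80) = 0.068.

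**3. Chance of a favourable result at n = 66.**

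| True control | Current rule, X ≥ 58 | X ≥ 59 |
|---|---|---|
| 80% | 6.8% | 3.3% |
| 85% | 33% | 21% |
| 88% | 60% | 46% |
| 90% | 79% | 66% |
| 94% | 98.3% | 95.7% |

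**4. Reversed test at n = 66.** H0: p ≤ p0. The cut-off r is the smallest value with P(X ≥ r | p0) ≤ 0.05; power = P(X ≥ r | 0.94). The documents give no margin, so p0 is an assumption and a range is shown.

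| p0 | Margin from 94% | Cut-off r | Type I error | Power at 94% | Exact lower bound at r |
|---|---|---|---|---|---|
| 80% | 14 points | 59 | 0.033 | 0.957 | 81.0% |
| 82% | 12 points | 60 | 0.035 | 0.900 | 82.8% |
| 84% | 10 points | 61 | 0.036 | 0.796 | 84.7% |
| 85% | 9 points | 62 | 0.023 | 0.637 | 86.7% |

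**5. If the number evaluable is not 66.** The paragraph opens with 100 patients and tests 66. With H0: p ≤ 0.80 the same method gives:

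| n | Cut-off | Type I error | Power at 94% |
|---|---|---|---|
| 60 | 54 | 0.031 | 0.933 |
| 65 | 58 | 0.037 | 0.960 |
| 70 | 62 | 0.044 | 0.976 |
| 100 | 87 | 0.047 | 0.997 |

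**The case against.** The strongest reply is that the harmful error is already limited. Power of 0.93 at 80% means a favourable result at a true 80% has about a 7% chance, so the rule is a disclosed screen with known properties and not an unpowered non-rejection. The cut-off of 59 also does not need reversed hypotheses: under the existing null, rejecting at 58 or fewer has type I error 0.043 and power 0.967 at 80%, within the stated limit. At the 80% limit the numerical change is one patient, and a favourable result would still occur 21% of the time at a true 85%. Both points are correct. They show that the change is cheap, but they do not turn non-rejection into evidence of equivalence.

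The plan never spells out what 58 or more means, and the objective is worded as feasibility. That leaves room to read the rule as a screen only. Against this, the section's opening claim is equivalence, and non-rejection is the only route the rule gives to it.

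The stakes are lower than in an untested de-escalation. Section 3.0 says this approach "does not deviate from one current standard of care" and lists it among current approaches, and Section 17.0 names only the 30Gy patients in Cohort 2 as departing from standard care. This limits the severity of the point.

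The contrast with the toxicity test is supporting evidence only, since that test seeks superiority and its null would naturally be no improvement. Finally, adopting 80% as the null does not itself justify a 14-point margin. That is right, and the justification has to come from the investigators.

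**Conclusion.** The concern holds and should be fixed. As written, the test cannot support the equivalence it sets out to show, and its boundary result would retain equivalence on data that fail to exclude 80% and do exclude 94%. The decision error at 80% is modest (6.8%). The larger problem is the conclusion drawn: a result that at best separates control from about 80% would be read as equivalence to 94%, and the chance of that reading is 33% at a true 85% and 79% at a true 90%.

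This rests on 66 evaluable patients, on exact binomial calculation, and on taking the 94% as fixed, as the plan does. It also rests on reading 58 or more as support for equivalence, which the text implies but does not state.

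**What to change.** In Section 14.0, restate the test as H0: 3-month nodal control ≤80% against H1: >80%, with 94% as the planning value. Conclude control above 80% only if at least 59 of 66 are controlled. Report the exact one-sided 95% lower bound whatever the result, and state that success means above 80%, not equivalence to 94%.

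Name the 14-point margin and justify it, or choose a narrower one and use the matching cut-off and power from the table of reversed tests. Give the source and sample size of the 94%. State that the cut-off will be recomputed by the same exact test if the number evaluable is not 66.

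**Cost.** With the 80% limit: SAP wording, a margin justification, and a cut-off of 59 in place of 58, with no extra patients. The chance of failing at a true 94% rises from 1.7% to 4.3%. A narrower margin costs power or patients. With an 85% limit, 66 patients give power 0.64, while 76 patients (at least 70 controlled, type I error 0.0497) give 0.83.

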Although a high loco-regional control rate of >90% is seen for oropharyngeal carcinoma treated with chemoradiation, patients still experience significant acute and late toxicities (13, 45). These toxicities are particularly concerning considering the increasing prevalence of HPV-associated head and neck carcinoma (42), particularly those of the base of tongue and tonsillar sites (both anatomical sites of the oropharynx) in individuals ages 20-44 in the United States (46). This latter statistic will ultimately coincide with longer-lasting long-term morbidities associated with OPSCC-targeted chemoradiation, which may have significant social and financial implications in the future (45) and an adverse effect on the long-term quality of life of patients who undergo this treatment.

Given the recent rise in HPV-related oropharyngeal carcinoma and the toxicities associated with the standard treatment course for this disease, an investigation into the efficacy and safety of treatment de-escalation to reduce the morbidity associated with the treatment of this disease is warranted. This is particularly true for the cohort of patients who present with HPV-related oropharyngeal carcinoma, as these patients are more likely to be younger and healthier than those presenting with non-HPV-related disease. When making the determination of which patients should undergo a less intense treatment regimen, it is important to make an evidence-guided selection. This cohort should only include patients most likely to: (1) respond efficaciously to treatment reduction, and (2) maximally benefit from a decrease in treatment-related toxicities. Otherwise, unwarranted tumor recurrences may result.

A number of investigations have established that the prognosis of patients with HPV-related oropharyngeal carcinoma is superior to that of patients with non-HPV-related oropharyngeal carcinoma (41, 44, and 47). In addition to HPV status serving as a mediator of overall prognosis and treatment response, it is well known that the presence of hypoxia renders tumor cells up to three times more resistant to ionizing radiation than aerobic cells (1-3). Hypoxia is also associated with a more aggressive and metastatically viable malignant phenotype, and has been shown in several studies to be an important determinant of loco-regional control of head and neck tumors (4, 5).

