9.0 TREATMENT/INTERVENTION PLAN

For patients in Cohort 1, there will be no change or intervention in a patient's treatment regime using chemoradiation where both the primary and the neck nodes receive 70Gy if the tumors are not associated with HPV or if there is no resolution of hypoxia on their repeat ¹⁸F-FMISO PET/CT scan.

Patients in Cohort 1 with tumors that are positive for HPV who exhibited no evidence of hypoxia on their baseline ¹⁸F-FMISO PET/CT scan or whose tumors have early resolution of hypoxia on their repeat early response ¹⁸F-FMISO PET/CT scan will undergo an alternative treatment where the primary tumor site receives 70Gy while the neck nodes receive 60Gy followed by a planned FDG PET/CT scan and observation.

Select Cohort 2 HPV+ tumors that demonstrate no evidence of hypoxia on an ¹⁸F-FMISO PET scan will receive 30Gy to the surgical bed and neck lymph nodes concurrent with standard chemotherapy followed by a 3 to 4 month post-treatment neck dissection. In patients who exhibit a complete response with this method of treatment, no further treatment is necessary. For patients within this select group who still have pathologic nodal disease, further standard chemoradiation will be given. All other patients in this cohort (i.e. those who are not in the select HPV+ tumor group outlined above) will receive standard of care treatment following their surgery.

Please note that for patients who receive a repeat ¹⁸F-FMISO PET/CT scan, the repeat ¹⁸F-FMISO PET/CT scan will only be performed 5-10 days into chemoradiotherapy treatment. For Cohort 1 patients, a repeat ¹⁸F-FMISO PET/CT scan will only be performed if the pretreatment baseline ¹⁸F-FMISO PET scan is positive for hypoxia.

Chemotherapy will be administered in two doses. Chemotherapy will begin +/- 3 days from the first day of radiation therapy. The second cycle of chemotherapy will begin 3 weeks later (+/- 5 days), although delays for safety (e.g, low white blood count, elevated creatinine) are allowed. Standard chemotherapy with either Cisplatin or Carboplatin/5-Fluorouracil is strongly recommended. Any other schedule (e.g, weekly chemotherapy) is discouraged and requires approval of the principal investigator.

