15.2 Randomization

Not applicable.

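### The late-toxicity log-rank test names no comparator, and the trial's own 70Gy patients cannot show whether a difference is due to dose

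*Combined protocol and SAP*

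**What the plan says.** Section 14.0 tests toxicity within 3 months by a one-sided one-sample proportion test. The 66 patients given 60Gy to the nodes are set against a historical 70Gy rate of about 75%, and success is 43 or fewer patients with a grade 2 or higher event.

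For later toxicity the plan changes method, because "censoring can be an issue so we will not apply the proportion test for toxicities after 3 months from chemoradiation". Data will be summarised descriptively and, when applicable, Kaplan-Meier estimation will be used with "log-rank tests to determine whether 60Gy results in lower toxicity". The sentence does not say which patients or curve the 60Gy group is tested against, and it gives no adjustment, event count or power.

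Sections 4.2 and 9.0 fix nodal dose in Cohort 1. There is no change from the regimen in which the primary and "neck nodes receive 70Gy if the tumors are not associated with HPV or if there is no resolution of hypoxia on their repeat" scan. HPV+ patients with no baseline hypoxia, or with early resolution, "will undergo an alternative treatment where the primary tumor site receives 70Gy while the neck nodes receive 60Gy". Section 15.2 states that randomization is not applicable. Section 3.0 says of HPV-related patients that "these patients are more likely to be younger and healthier than those presenting with non-HPV-related disease".

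**The concern.** A log-rank test needs a second survival curve. The 3-month test gets its reference from a fixed historical rate. The late-toxicity sentence drops that rate and puts nothing in its place. The 70Gy patients to hand are those in the trial, and they are on 70Gy because their HPV or hypoxia status kept them there. A lower late-toxicity curve at 60Gy could then reflect who was selected for 60Gy and not the dose.

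This matters because fewer treatment-related complications are part of the stated 60Gy hypothesis, and long-term morbidity is central to the case for de-escalation in Section 3.0. An apparent late benefit would be read as evidence for the lower dose.

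**Working it through.** **1. The plan's nearest toxicity figure reproduces.** The log-rank test has no stated operating characteristics, so the check is on the 3-month rule. With X binomial, n = 66 and success if X ≤ 43:
- P(X ≤ 43) at 75% = 0.048 (plan: below 0.05).
- P(X ≤ 43) at 60% = 0.836 (plan: 0.84).

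The 3-month rule is sound on its own terms.

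**2. Who is on each dose.** From Sections 4.2 and 9.0:

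| Cohort 1 status | Nodal dose by rule |
|---|---|
| HPV+, no baseline hypoxia | 60Gy |
| HPV+, early resolution on the repeat scan | 60Gy |
| HPV+, hypoxia not resolved | 70Gy |
| HPV- | 70Gy |

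No row appears under both doses. The planned number of HPV+ patients with absent or resolved hypoxia on 70Gy is 0.

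**3. Size of the imbalance.** Section 14.0 gives 100 HPV+ and 50 HPV- patients, and 66 patients on 60Gy.
- HPV+ on 70Gy: 100 − 66 = 34 (inferred; no section states it).
- All on 70Gy: 34 + 50 = 84.
- HPV- share: 50/84 = 59.5% on 70Gy, 0/66 = 0% on 60Gy.

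Section 14.0 also speaks of 100 HPV+ patients with negative or resolved scans. If all 100 received 60Gy, the 70Gy group would be the 50 HPV- patients only, and the imbalance would be complete.

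**4. What the imbalance could do to the test.** Assumptions, none from the documents: exponential event times; 40% of HPV+ patients with an event by 2 years, so the hazard is −ln(0.60)/2 = 0.255 per year; an HPV- hazard of HR × 0.255; no dose effect; no losses before 2 years. The 2-year horizon is the chart-review period in Section 1.0. The HPV- 2-year rate is 1 − 0.60^HR, and the 70Gy average is (34 × 0.40 + 50 × HPV- rate)/84.

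| HPV- hazard ratio | HPV- 2-year rate | 70Gy average | 60Gy | Two-sided p<0.05 | One-sided 0.05, favouring 60Gy |
|---|---|---|---|---|---|
| 1.3 | 48.5% | 45.1% | 40% | about 9% | about 15% |
| 1.5 | 53.5% | 48.1% | 40% | about 17% | about 25% |
| 2.0 | 64.0% | 54.3% | 40% | about 43% | about 55% |

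The last two columns are simulated rejection rates for 66 v 84 patients; repeat runs differ by a point or two. One-sided 0.05 is shown because the 3-month test takes that form. With no HPV effect, rejection stays at the nominal level (4–5%).

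**5. Restricting to HPV+.** For 66 v 34 HPV+ patients under the same model, two-sided rejection is about 5%, which is nominal. The HPV imbalance is gone, but all 66 have absent or resolved hypoxia and all 34 have unresolved hypoxia, so dose and hypoxia status still cannot be separated.

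**The case against.** The strongest reply is that the plan never says the log-rank test uses concurrent patients. The toxicity text begins from historical results in similar 70Gy patients, and the late-toxicity sentence replaces that test, so a historical comparison may be intended. This stands as a reading: a reader might infer that the plan commits itself to a concurrent comparison, and the documents do not settle that. But no late-toxicity series or curve is named. The one 70Gy series described, in Section 3.0, is the first 20 patients of a protocol open regardless of HPV status, with no late-toxicity data given.

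A reader might also infer that no adjustment could help. That is too strong. The mechanism the documents suggest, younger and healthier HPV+ patients, works through HPV status, and restriction to HPV+ removes it. What remains is hypoxia status. The documents link hypoxia to tumor radioresistance and aggressiveness, not to normal-tissue toxicity, so confounding there is possible but not shown.

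Section 3.0 calls 60Gy "the option of an alternative standard approach to the treatment of oropharyngeal carcinoma", so an eligible patient might stay on 70Gy. No section plans, counts or names such patients as a comparator.

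Finally, the test is conditional and comes after descriptive summaries. This limits the consequence. But the words when applicable govern whether the test is run, not what it would be said to determine. The general caveat in Section 14.0 about limited power does not help either, because the problem is bias.

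**Conclusion.** The point holds in this form: the late-toxicity log-rank test has no named comparator, and if it is run against the trial's own 70Gy patients it cannot support the dose conclusion the plan assigns to it. That follows from the allocation rules alone.

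The size is less certain. The 60% v 0% HPV- imbalance rests on the inferred 34. The rejection rates of about 9%, 17% and 43% rest on an assumed event rate and assumed hazard ratios. The documents say HPV-related patients tend to be younger and healthier; they do not say HPV- patients have more late toxicity. The figures show what the imbalance could do, not what it will do.

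A reader might extend the point to the 3-month toxicity result. That is not supported: the 3-month rule uses a fixed historical rate, and its figures reproduce. The change is worth making, but no formal decision rule depends on it.

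**What to change.** In Section 14.0:
- Delete the statement that log-rank tests will determine whether 60Gy lowers late toxicity.
- Report the cumulative incidence of late grade 2 or higher toxicity in the 60Gy group with a 95% CI, treating death as a competing event.
- Label any concurrent 60Gy and 70Gy curves as descriptive, and show them by HPV status.
- Make a dose comparison only if patient-level time-to-toxicity data exist for a named historical series of HPV+ patients treated with 70Gy. The documents do not show that such data exist. Nor do they state that the 75% benchmark comes from HPV+ patients, so its source should not be assumed to be that series.

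The cost is a wording change, and one inferential claim becomes descriptive. Treatment, data collection and the 3-month rule (43 or fewer of 66) stay as they are.
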